2.0 OBJECTIVES AND SCIENTIFIC AIMS

Primary Objectives

- To compare 24-30 month post-SBRT prostate 12 core biopsy outcomes between intermediate risk patients treated with SBRT and short course ADT versus SBRT alone.

Secondary Objectives

- To assess whether the addition of 6 months of ADT with high dose SBRT decreases incident rates of biochemical failure and distant failure, or improves survival rate for intermediate risk prostate cancer patients compared to SBRT alone.
- To assess the differences in short-term and long-term quality of life outcomes by comparing EPIC-26, IPSS, and SF-12 survey results between intermediate risk prostate cancer patients treated with SBRT + short course ADT versus SBRT alone.

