3.3 Study Rationale

To date there have been no studies exploring the impact of short course ADT for intermediate risk patients who are treated with SBRT. On the one hand the use of high dose SBRT with its greater radiobiological dose delivery may obviate the need for short course ADT and potentially reduce the deleterious impact this therapy would have on the quality of life of the individual patient. On the other hand, the addition of short course ADT even in the setting of high dose SBRT may further improve survival outcomes especially among the cohort of intermediate risk patients with more unfavorable disease characteristics as has been demonstrated in published Phase III trials when conventionally fractionated radiotherapy was used (1, 2). With the increasing number of patients being treated with SBRT at our institution and in the United States, this issue is of significant clinical importance. This study will evaluate the tumor control outcomes in each group and as the primary objective of this study we will evaluate local tumor control with a 2- year post treatment biopsy considered to represent an excellent surrogate endpoint for local disease control and more reflective of this endpoint than PSA-relapse-free survival. This biopsy endpoint has been successfully used in our Phase I dose escalation study (IRB- 09-035) evaluating local control in SBRT treatment patients. However, in addition to 2 year biopsy outcomes, biochemical control and distant metastases-free survival will also be evaluated.

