4.0 OVERVIEW OF STUDY DESIGN/INTERVENTION

4.1 Design

For this proposed Phase III study, intermediate risk patients will be randomized to received 6 months of ADT which would be given 3 months prior to planned SBRT to the prostate and 3 months during/following SBRT. ADT will be administered via Degarelix monthly injections. SBRT will be delivered with a prescription dose of 8 Gy x 5 prescribed to the planning target volume. Inter-fraction motion targeting and target position correction will be utilized as is routine in our department during the treatment SBRT.

The primary end-point of this study is the proportion of patients who have positive 2-year post-treatment prostate biopsies. Based on our previous published experience, we expect that the 2-year rate of a positive biopsy using ADT with ultra-hypofractionated SBRT for intermediate risk features would be 15% compared to 35% for those patients treated with SBRT alone. We anticipate we would require powering the study with 100 patients in each arm. Randomization will be stratified by favorable-intermediate and unfavorable-intermediate risk status (unfavorable-intermediate risk will be defined as patients having Gleason 4+3, >50% positive biopsy cores or 2 intermediate risk factors combined such as Gleason 7 and PSA > 10 ng/ml).

The primary endpoint is the 2-year biopsy which is generally scheduled at the end of the second year. However, we have provided some flexibility as to prevent prospective and retrospective deviations. Therefore, we have chosen to allow the primary endpoint biopsy to occur between 24-30 months which we believe is reasonable based on our clinical experience.

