8.0 PRETREATMENT EVALUATION

The following must be completed prior to randomization:

- MSKCC pathology review confirming cancer
- The following screening tests and assessments should be performed within 8 weeks prior to randomization to confirm eligibility:
 - Full medical history and physical exam, including DRE and performance status
 - MRI of the prostate and pelvis within 6 months of randomization. (CT of the pelvis with contrast may be performed if MRI is contraindicated)
 - Radionuclide bone scan if there is suspicion of bone metastases within 6 months of randomization.
 - Lab tests:
 - PSA
 - Baseline CBC, CMP (Na, K, Cl, CO₂, Ca, T. Protein, Albumen, Creatinine, Glucose, BUN, Alk Phos, ALT, AST, T. Bili), Conj. Bili,

- Testosterone level
- Questionnaires:
 - IPSS documenting score < 20
 - EPIC
 - SF-12

Once eligibility is confirmed, the patient should undergo randomization.

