11.0 TOXICITIES/SIDE EFFECTS

In each arm standard SBRT will be used delivering 40 Gy in 5 fractions to the prostate and seminal vesicles and patients will be randomized to receive 6 months of ADT using Degarelix monthly injections or SBRT alone without ADT. ADT administration is routine and its side effect profile well recognized and established. Side effects of ADT (Degarelix) include hot flashes, fatigue, weight gain, loss of libido, muscle tone decrease and gynecomastia. These side effects generally reverse 6-12 months after cessation of ADT. Any urinary or rectal toxicity that is grade 3 or higher will be considered an adverse event.

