14.0 BIOSTATISTICS

The primary objective of this phase III trial is to compare 2-year biopsy positivity rate of intermediate risk prostate cancer patients treated with SBRT + short course ADT versus SBRT alone. The 2-year biopsy positivity rate will be calculated in each arm as a proportion of patients whose 2-year (from the end of SBRT) biopsy result is positive over patients who have 2-year biopsy results examined or whose 2-year biopsy results are regarded as positive (see the replacement rule below). We plan to analyze an evaluable sample of 200 patients, randomized in a 1:1 ratio to the two arms. This sample size has a power greater than 0.90 and type 1 error rate of 0.05 if the true 2-year biopsy positivity rates are 35% and 15% respectively, for the two arms using a two-sided, two-sample proportion test. This test will also be adjusted for the randomization stratification variables. Patients who died due to disease within 2 years from the end of SBRT will be regarded as having a positive biopsy. Patients who died not due to disease or are lost to follow-up within 2 years from the end of SBRT without any sign of progression will be replaced. To this end we will enroll an additional 10% patients upfront so the total sample size is 223. However, only the first 200 evaluable patients will be counted towards the primary endpoint. One interim analyses and one final analysis are planned (using equal spacing of looks) and the null hypothesis that the two arms have the same 2-year biopsy positivity rates will be rejected at these two looks if the p-values are <0.003 and <0.049, respectively, based on the Lan-DeMets alpha spending function approach. We expect that 100 patients will be enrolled each year, 50 from MSK and 50 between all regional sites. Therefore we anticipate to complete the enrollment in 2-3 years, plus an additional 2-year mandatory follow-up.

For the secondary objectives, the cumulative incidence rates of biochemical failure and distant failure will be evaluated by the competing risks method and Gray's test will be used to compare the two arms. Overall survival rates will be estimated by Kaplan-Meier method and compared by log-rank tests. QOL outcomes will be summarized and tabulated. Results from the two arms will be compared by Wilcoxon rank sum tests at time points when these surveys are conducted. All patients will be analyzed for the secondary objectives.

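### The quality-of-life comparison, as written, makes no use of the baseline scores and plans no between-arm difference with a confidence interval

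*Combined protocol and SAP*

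**What the plan says.** Section 2.0 makes quality of life a secondary objective: "To assess the differences in short-term and long-term quality of life outcomes", using EPIC-26, IPSS and SF-12. Section 3.3 gives the reason: SBRT at high dose might make ADT unnecessary and "potentially reduce the deleterious impact this therapy would have on the quality of life of the individual patient".

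Section 14.0 gives the analysis in two sentences: "QOL outcomes will be summarized and tabulated", and "Results from the two arms will be compared by Wilcoxon rank sum tests at time points when these surveys are conducted". It adds that all patients are analyzed for the secondary objectives. Adjustment for the stratification variable is stated for the primary biopsy test; nothing similar is stated for quality of life.

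The baseline scores will exist. Section 8.0 lists IPSS, EPIC and SF-12 under "The following screening tests and assessments should be performed within 8 weeks prior to randomization to confirm eligibility". Table 1 in Section 10.2 marks the three surveys before treatment, during radiation and at follow-up. Only the follow-up months are unstated; Sections 1.0 and 4.2 put visits every 6 months.

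**The concern.** The clinical question is not whether ADT has side effects. Section 11.0 already says that they "include hot flashes, fatigue, weight gain, loss of libido, muscle tone decrease and gynecomastia" and that "These side effects generally reverse 6-12 months after cessation of ADT". The open question is how much worse quality of life is with ADT, at which visits, and how precisely that is known. A rank-sum p-value does not answer it. Tables by arm show each arm's level, but not the precision of the difference.

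The plan also leaves unused the covariate most likely to sharpen the comparison, namely each man's own score before randomization. And because no domain or visit is singled out, it does not say which of the many tests carries the conclusion on this objective.

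**Working it through.** **Figures in the plan.** None is given for quality of life. The nearest are for the biopsy endpoint, and they reproduce: 100 per arm at 35% against 15%, two-sided 0.05, gives power 0.910 (stated as above 0.90), and 200/0.90 = 222.2, rounded up to 223.

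**Number of tests.** Section 5.0 gives 5 EPIC-26 domains, 2 SF-12 summaries and 1 IPSS index: 8 scores. Surveys after baseline, if done at every visit: during SBRT and at 6, 12, 18 and 24 months, so 5 (an assumption). 8 × 5 = 40 tests.

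**Assumed inputs.** 100 men per arm answer a survey (about 90% of 223). Correlation r between baseline and follow-up is 0.3, 0.5 or 0.7. The documents give no correlation, effect size or ceiling rate.

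**Interval width, normal scores.** The unadjusted 95% half-width is 1.96 × √(2/100) = 0.277 SD. Baseline adjustment multiplies it by √(1 − r²):
- r = 0.3: 0.277 × 0.954 = 0.264 SD
- r = 0.5: 0.277 × 0.866 = 0.240 SD
- r = 0.7: 0.277 × 0.714 = 0.198 SD

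Simulation (10,000 replicates) gives adjusted-to-unadjusted ratios of 0.957/0.869/0.717, so the interval narrows by about 4/13/28%. With 69% of scores at a ceiling the ratios are 0.979/0.926/0.812, or about 2/7/19%. The gain in width does not depend on the size of the effect.

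**Power at an assumed 0.4 SD, one visit, normal scores.** For Wilcoxon, 0.4 × √(100/2) × √(3/π) = 2.76, and Φ(2.76 − 1.96) = 0.789. For linear adjustment (ANCOVA) at r = 0.5, 0.4 × √50 / 0.866 = 3.27, and Φ(3.27 − 1.96) = 0.904. Simulated power in %, for r = 0.3/0.5/0.7:

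| Setting | Wilcoxon | ANCOVA | Rank-based adjustment (Quade) |
|---|---|---|---|
| Normal | 78/78/78 | 83/90/98 | 81/88/96 |
| 50% at bound, effect away from it | 73/74/73 | 73/79/90 | 76/82/91 |
| 69% at bound, effect away from it | 67/66/66 | 63/68/79 | 68/72/81 |
| 50% at bound, effect toward it | 68/68/68 | 65/71/84 | 70/76/86 |
| 69% at bound, effect toward it | 56/57/56 | 51/55/65 | 58/63/70 |

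Type I error was 0.047 to 0.055 for all three methods. Linear adjustment loses power at low r with heavy ceilings. The rank-based test gained in every setting, but by only about 1 to 3 points at r = 0.3.

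**Larger effects.** At 0.6 SD, Wilcoxon power is already 98–99% (normal), 97–98% (50% at ceiling) and 95% (69% at ceiling), so little power is left to gain.

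**If change from baseline is meant.** Its variance relative to raw scores is 2(1 − r) = 1.40/1.00/0.60, against 1 − r² = 0.91/0.75/0.51 for adjustment. Adjustment is more precise under either reading.

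**Age of baseline.** ADT is "given 3 months prior to planned SBRT to the prostate and 3 months during/following SBRT", so at the on-treatment survey the baseline is about 3 months older in that arm and may correlate less. With r = 0.5 in the SBRT arm and 0.3 in the ADT arm, ANCOVA power is 0.871 against 0.789 for Wilcoxon. Type I error stayed at 0.044 to 0.051 over the unequal settings.

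**The case against.** Wilcoxon is a defensible, robust choice for bounded and skewed scores, and under randomization it is valid without baseline data. Section 14.0 is brief throughout and states no confidence interval for any endpoint, so the omission is not peculiar to quality of life, and nothing forbids reporting differences. The power argument rests on assumed values: if the hormonal or sexual effects exceed 0.4 SD, the gain largely disappears, and linear adjustment can do harm near a score bound. Quade's test gives only a p-value, so it does not supply the missing estimate.

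Most of this stands. It limits the power argument and means that linear adjustment should not govern every score. It does not touch the interval: the gain in width holds at any effect size, and the absence of a planned difference with a CI does not depend on r.

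A reader might infer more than the documents support:
- *That the tests are wrong, or that the primary result is at risk.* Neither follows.
- *That about 40 tests make a false finding near certain.* 1 − 0.95⁴⁰ = 0.87 requires independent tests and no true difference on any score. The scores are correlated, and Section 11.0 expects real effects of ADT.
- *That the baseline scores are not used at all.* Baseline IPSS serves as an eligibility limit (Sections 6.1 and 8.0), and the tabulations may include baseline. The gap is in the between-arm comparison.
- *That the survey times are missing.* Only the follow-up months are unstated, and the 6-month visit interval largely implies them.

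**Conclusion.** The point holds as a matter of precision and interpretability for a secondary objective that is part of the trial's rationale. As written, the plan would give p-values and tables by arm, but no between-arm difference with its uncertainty, and would forgo an interval about 4 to 28% narrower (normal scores) or 2 to 19% narrower (69% at ceiling) over r = 0.3 to 0.7. The power gain is secondary: modest at r = 0.3, larger at higher r, and almost nil at 0.6 SD or more. These sizes rest on the assumed r, ceiling rates and 100 men per arm; the absence of a planned estimate rests on the text alone. Naming a key domain and visit is desirable, but is mostly a matter of missing detail.

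**What to change.** In Section 14.0:
- For each score and visit, report the between-arm difference with a 95% CI from a model adjusted for baseline score and randomization risk stratum, either per-visit ANCOVA or repeated measures with arm-by-visit and baseline-by-visit terms. If repeated measures is used, state that it assumes data missing at random and does not cure informative dropout.
- For scores with heavy ceiling or floor effects, let a rank test govern the p-value, preferably baseline-adjusted (e.g. Quade's), and take the CI from the adjusted model. Say in advance how such scores are identified, so that there is a rule if the two disagree.
- Keep the planned Wilcoxon tests as a sensitivity analysis.
- Preferably name one key domain and visit before results are seen, label the rest descriptive, and list the follow-up survey months.

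The cost is SAP wording, slightly more analysis work and a model assumption. Linear adjustment alone can lose power near a bound at low r (for example 56% to 51% with 69% at the bound, r = 0.3 and the effect toward it), which is why the rank test should govern there. No new patients, visits or data are needed.

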15.0 RESEARCH PARTICIPANT REGISTRATION AND RANDOMIZATION PROCEDURES

15.1 Research Participant Registration

Confirm eligibility as defined in the section entitled Inclusion/Exclusion Criteria. Obtain informed consent, by following procedures defined in section entitled Informed Consent Procedures. During the registration process registering individuals will be required to complete a protocol specific Eligibility Checklist. The individual signing the Eligibility Checklist is confirming that the participant is eligible to enroll in the study. Study staff are responsible for ensuring that all institutional requirements necessary to enroll a participant to the study have been completed. See related Clinical Research Policy and Procedure #401 (Protocol Participant Registration).

15.2 Randomization

Patients will be randomized to receive ADT+SBRT, or SBRT alone. Immediately after consent is obtained, the RSA at MSKCC will register participants in the Clinical Trials Management System (CTMS). Once the participant's eligibility is established the registration will be finalized and the participants will be randomized using the Clinical Research Database (CRDB). Randomization will be accomplished by the method of random permuted block, and will be stratified by favorable vs unfavorable intermediate risk. After the treatment

arm is determined by randomization, the RSA will notify physicians at MSKCC of the treatment arm and participant ID via email within 24 hours of randomization.

16.0 DATA MANAGEMENT ISSUES

A Research Study Assistant (RSA) will be assigned to the study. The responsibilities of the RSA include project compliance, data collection, abstraction and entry, data reporting, regulatory monitoring, problem resolution and prioritization, and coordinate the activities of the protocol study team.

The data collected for this study will be entered into Medidata RAVE. Source documentation will be available to support the computerized patient record. All research material from this study will be handled with the same confidentiality as patient's other medical data. Data collected will include participant demographics, PRO outcomes data, PSA and testosterone values, and biopsy results.

16.1 Quality Assurance

Eligibility of patients will be verified with the corresponding investigator. Only the designated investigators can obtain informed consent.

There are several different mechanisms by which clinical trials are monitored for data, safety and quality. Institutional processes are in place for quality assurance (e.g., protocol monitoring, compliance and data verification audits, therapeutic response, and staff education on clinical research QA) and departmental procedures for quality control, and two institutional committees are responsible for monitoring the activities of our clinical trials programs. The committees, *Data and Safety Monitoring Committee (DSMC)* for Phase I and II clinical trials, and the *Data and Safety Monitoring Board (DSMB)* for Phase III clinical trials, report to the Center's Research Council and Institutional Review Board (see section 16.2).

16.2 Data and Safety Monitoring

The Data and Safety Monitoring (DSM) Plans at MSK were approved by the National Cancer Institute in September 2001. The plans address the new policies set forth by the NCI in the document entitled "Policy of the National Cancer Institute for Data and Safety Monitoring of Clinical Trials," which can be found at:

<http://cancertrials.nci.nih.gov/researchers/dsm/index.html>.

The DSM Plans at MSK were established and are monitored by the Office of Clinical Research. The MSK Data and Safety Monitoring Plans can be found on the MSK Intranet at: <https://one.mskcc.org/sites/pub/clinresearch/Documents/MSKCC%20Data%20and%20Safety%20Monitoring%20Plans.pdf>.

17.0 PROTECTION OF HUMAN SUBJECTS

Patient Confidentiality: Patient/subject privacy and confidentiality will be maintained according to MSK guidelines and all data derived from this study will be kept in a secure database. All data and results will be anonymously reported with regard to individual subjects.

Voluntary nature of the study: Subjects will be made aware of the voluntary nature of the study as part of the informed consent process. They will be allowed to withdraw participation at any time without the risk of alteration in the quality of their medical care.

The subjects will be responsible for all charges associated with the items that are part of the routine clinical care, including the post treatment 12 core biopsy and the follow up PSA measurements. Subjects will not be compensated for their participation. If the patient is injured as a result of being in this study, emergency care, hospitalization, and outpatient care will be made available by the hospital and billed to the patient and his insurance company as standard of care.

17.1 Privacy

MSK's Privacy Office may allow the use and disclosure of protected health information pursuant to a completed and signed Research Authorization form. The use and disclosure of protected health information will be limited to the individuals described in the Research Authorization form. A Research Authorization form must be completed by the Principal Investigator and approved by the IRB and Privacy Board (IRB/PB).

17.2 Serious Adverse Event (SAE) Reporting

An adverse event is considered serious if it results in ANY of the following outcomes:

- Death
- A life-threatening adverse event
- An adverse event that results in inpatient hospitalization or prolongation of existing hospitalization
- A persistent or significant incapacity or substantial disruption of the ability to conduct normal life functions
- A congenital anomaly/birth defect
- Important Medical Events (IME) that may not result in death, be life threatening, or require hospitalization may be considered serious when, based upon medical judgment, they may jeopardize the patient or subject and may require medical or surgical intervention to prevent one of the outcomes listed in this definition

Note: Hospital admission for a planned procedure/disease treatment is not considered an SAE.

SAE reporting is required as soon as the participant signs consent. SAE reporting is required for 30-days after the participant's last investigational treatment or intervention. Any events that occur after the 30-day period and that are at least possibly related to protocol treatment must be reported.

If an SAE requires submission to the IRB office per IRB SOP RR-408 'Reporting of Serious Adverse Events', the SAE report must be sent to the IRB within 5 calendar days of the event. The IRB requires a Clinical Research Database (CRDB) SAE report is submitted electronically to the SAE Office as follows:

For IND/IDE trials: Reports that include a Grade 5 SAE should be sent to [contact]. All other reports should be sent to [contact].

For all other trials: Reports that include a Grade 5 SAE should be sent to [contact]. All other reports should be sent to [contact].

The report should contain the following information:

Fields populated from CRDB:

- Subject's initials
- Medical record number
- Disease/histology (if applicable)
- Protocol number and title

Data needing to be entered:

- The date the adverse event occurred
- The adverse event
- The grade of the event
- Relationship of the adverse event to the treatment (drug, device, or intervention)
- If the AE was expected
- The severity of the AE
- The intervention
- Detailed text that includes the following
 - A explanation of how the AE was handled
 - A description of the subject's condition
 - Indication if the subject remains on the study
- If an amendment will need to be made to the protocol and/or consent form
- If the SAE is an Unanticipated Problem

The PI's signature and the date it was signed are required on the completed report.

For IND/IDE protocols:

The CRDB SAE report should be completed as per above instructions. If appropriate, the report will be forwarded to the FDA by the SAE staff through the IND Office

17.2.1

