4.2 Intervention

Eligible patients with intermediate risk disease will be randomized to ADT with SBRT versus SBRT alone. The ADT patients will be treated with monthly degarelix injections. After three months (+/- 1 month) have elapsed, these patients as per routine would undergo fiducial marker placement followed by simulation and SBRT to follow. For this cohort ADT will continue until 6 months of Degarelix is administered. If a patient develops an allergic reaction to the Degarelix injection, he may be switched to Leuprolide acetate monthly injections in its place.

For patients treated with SBRT alone referral will be made for fiducial marker placement with simulation and SBRT to follow. Patients will then be followed at 6 month intervals with routine serum PSA and testosterone testing. All patients will undergo a post-SBRT standard 12 core prostate biopsy at 24-30 months after completion of SBRT to evaluate local tumor control status.

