9.0 TREATMENT/INTERVENTION PLAN

Androgen Deprivation Therapy Arm: Within two weeks prior to the first injection, patients will obtain routine blood tests including CBC and liver function tests and testosterone levels. Degarelix injections will be administered in the radiation oncology clinics monthly. The first injection is administered as a boost, 240 mg given as two subcutaneous injections of 120 mg at a concentration of 40 mg/mL which is then followed by 80 mg given as one subcutaneous injection at a concentration of 20 mg/mL every 28 days (+/- 7days). In 10% of patients a skin rash could develop at the injection site. If this is noted and symptomatic for the patient the injection could be switched to monthly Lupron intramuscular injections (7.5.mg).

Study treatment: Stereotactic, Ultra-Fractionated Radiotherapy (same for each arm)

Intensity-modulated, image-guided, ultra-hypofractionated external beam radiotherapy will incorporate prostate and seminal vesicles and this planning target volume will receive 8 Gy x 5 fractions. As per routine for intermediate risk patients, the lymph nodes will not be included within the treatment portal.

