10.2 Evaluation during Follow-Up

- Physical exam
- Performance status
- Clinical evaluation for late urinary, rectal toxicity and sexual dysfunction per standard CTCAE assessments and grading.
- PSA
- Serum Testosterone
- EPIC – 26
- SF-12
- IPSS
- Prostate biopsy, 24-30 months post SBRT

Table 1. Schedule of assessments

	Pre-Treatment	During Radiation Therapy	Follow up
	Within 8 weeks prior to study randomization	Within 2 week prior to the initiation of Degarelix ¹	
Informed consent	X		
Medical history	X		
Physical exam	X		X
Digital rectal exam	X		
Performance status	X		X
Histologic or pathologic confirmation of disease	X ²		
MRI prostate/pelvis within 6 months of randomization	X ³		
Bone scan within 6 months of randomization if determined necessary	X		
EPIC-26	X	X ⁴	X
SF-12	X	X ⁴	X
IPSS	X	X ⁴	X
PSA	X	X	X
CBC	X	X	
Comp	X	X	
Liver function tests	X	X	
Serum testosterone	X	X	X
Toxicity assessment			X
Degarelix		X ⁵	
Fiducial marker placement		X ⁶	
Radiation therapy		X'	
Biopsy			X ⁸

1. For patients randomized to the ADT + SBRT arm
2. Histologic or pathologic confirmation of disease can be done anytime prior to randomization.
3. CT of the pelvis with contrast may be performed if MRI is contraindicated.
4. To be completed during treatment, at the 3rd of 5th fraction of later
5. Degarelix will be given monthly (+/- 7 days), 3 months before and 3 months after radiation therapy.
6. Fiducial markers will be placed 3 days before simulation.
7. Radiation therapy will be given every other day.
8. Prostate post-treatment biopsy will be performed once at 24-30 months post SBRT.

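### All-cause SAE reporting ends 30 days after each patient's last treatment, so it runs longer in the ADT arm: about 2 to 3.5 times as long from randomisation under stated assumptions

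*Combined protocol and SAP*

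**What the plan says.** Section 17.2 sets three rules.

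- Start: "SAE reporting is required as soon as the participant signs consent".
- End of all-cause reporting: "SAE reporting is required for 30-days after the participant's last investigational treatment or intervention".
- Afterwards: "Any events that occur after the 30-day period and that are at least possibly related to protocol treatment must be reported". This has no end date and applies to both arms.

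No calendar end is common to the two arms.

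The treatment schedules differ by arm. For ADT, section 4.2 says "For this cohort ADT will continue until 6 months of Degarelix is administered", and places fiducials, simulation and SBRT as follows: "After three months (+/- 1 month) have elapsed". Table 1, footnote 5 adds: "Degarelix will be given monthly (+/- 7 days), 3 months before and 3 months after radiation therapy". Patients on SBRT alone are referred for fiducials, then have simulation and five fractions.

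The protocol describes no blinding. Under section 15.2, physicians are told the arm after randomisation. Section 14.0 plans no comparison of SAEs by arm. Section 17.0, in a paragraph on who pays, lists the biopsy under "routine clinical care, including the post treatment 12 core biopsy".

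**The concern.** An all-cause window tied to the last treatment is only as equal between arms as the treatment durations, and here one arm is treated for about six months and the other for a few weeks. With the same true risk of unrelated serious events, the ADT arm would report more of them simply because it is watched longer.

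Outside the window, reporting depends on a relatedness judgement by investigators who know the arm, and that judgement may itself differ between arms.

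Other safety collection does not clearly fill the gap. Follow-up CTCAE grading (section 10.2) names urinary, rectal and sexual toxicity. Section 11.0 treats grade 3 or higher urinary or rectal toxicity as an adverse event. For serious events of other kinds, section 17.2 is the only reporting route that the protocol describes.

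At stake is how any SAE table by arm can be read, whether by the DSMB that oversees phase III trials (section 16.1) or in the final report.

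**Working it through.** The plan gives no window length by arm, so there is no stated figure to reproduce. The lengths below are built from the schedule.

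**Inputs from the protocol**
- Degarelix every 28 days (+/- 7) (section 9.0), for 6 months (section 4.2)
- Fiducials at least 3 days before simulation (section 9.1)
- First fraction 14 (+/- 7) days after simulation (section 9.3)
- Five fractions every other day (section 5.0), so 8 days from first to last

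**Assumptions**
- Six doses; the number is not stated
- First dose on the day of randomisation
- A wait of 0 to 28 days from randomisation to fiducials in SBRT alone; no limit is stated

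**ADT arm, closing day from randomisation**
- Last dose at 5 x 28 = day 140; window closes at 140 + 30 = day 170.
- Seven doses: 6 x 28 + 30 = day 198.
- Six doses with every interval at 21 or 35 days: 5 x 21 + 30 = day 135, or 5 x 35 + 30 = day 205.
- SBRT late enough to be the last treatment (fiducials at 4 calendar months, day 122): 122 + 3 + 21 + 8 + 30 = day 184.

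**SBRT alone, closing day = wait + 3 + (7 to 21) + 8 + 30**

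| Wait (days) | Closing day, central (range) | Ratio of 170 to it, central (range) |
|---|---|---|
| 0 | 55 (48-62) | 3.1 (3.5-2.7) |
| 14 | 69 (62-76) | 2.5 (2.7-2.2) |
| 28 | 83 (76-90) | 2.0 (2.2-1.9) |

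The absolute gap is 170 - 48 = 122 days down to 170 - 90 = 80 days. A longer wait narrows it: 56 days gives a central closing day of 111 and a ratio of 1.5. A 14-day delay to the first dose widens it: day 184 against days 48 to 90 gives 3.8 to 2.0.

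**From consent.** An equal lead time is added to both arms, which lowers the ratio and leaves the gap unchanged. A 28-day lead with no wait gives (170 + 28)/(55 + 28) = 198/83 = 2.4. With a 28-day wait as well, it gives 198/111 = 1.8.

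**Coverage after SBRT.** In SBRT alone it is 30 days. In the ADT arm, counting a month as 28 days:
- Central: SBRT ends at 84 + 3 + 14 + 8 = day 109, so coverage is 170 - 109 = 61 days.
- Earliest: 56 + 3 + 7 + 8 = day 74, so 170 - 74 = 96 days.
- Latest: 112 + 3 + 21 + 8 = day 144. The last fraction now follows the last dose, so coverage is 30 days, as in the other arm.

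**Illustrative counts.** Section 14.0 enrols 223 (200/0.90 = 222.2, rounded up), or 111.5 per arm. With an assumed rate of unrelated SAEs equal in both arms, expected reports = 111.5 x (closing day/365) x rate.

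| Rate per patient-year | ADT arm (day 170) | SBRT alone (days 48-90) |
|---|---|---|
| 0.05 | 2.6 | 0.7-1.4 |
| 0.10 | 5.2 | 1.5-2.7 |
| 0.20 | 10.4 | 2.9-5.5 |

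**The case against.** The strongest case against is that nothing planned depends on this. Section 2.0 has no SAE or toxicity objective and section 14.0 has no SAE comparison. Section 17.2 is an institutional reporting rule, not an endpoint definition. Section 3.3 frames the harm of ADT as loss of quality of life, which is measured on the same instruments in both arms. What the DSMB tabulates is left to institutional plans that the protocol does not reproduce. All of this stands, and it limits the consequence: a reader might infer that a planned safety comparison is invalid or that the DSMB will see a false excess, and the documents support neither.

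A reader might also infer that SAE reporting simply stops. It does not: possibly related events stay reportable without limit in both arms. A flat threefold difference is equally tempting, but it needs six doses, ADT starting at randomisation and no wait for fiducials.

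It can also be said that event dates are recorded, so the analysis could truncate to the shorter window or use person-time rates. That helps only in part. Truncating at day 48 to 90 would remove most or all of the period after SBRT in the ADT arm, where SBRT ends about day 109 (74-144). Person-time rates remove the effect of window length fully only if the event rate is roughly constant over time.

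On the biopsy, a reader might infer that its complications are excluded from reporting. The routine-care wording is about billing and does not define relatedness. Section 17.2 refers to treatment or intervention in one sentence and to protocol treatment in the next, without saying where the biopsy belongs. If it counted as an intervention, both windows would run past 24 months and the imbalance would largely disappear. The ordinary reading is study treatment, so this remains a smaller wording gap.

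**Conclusion.** The concern holds in limited form. A stated rule gives unequal all-cause SAE ascertainment in a trial where physicians know the arm. From randomisation the window is about 2 to 3.5 times as long in the ADT arm, on the assumptions of six doses 28 days apart from randomisation and a 0 to 28 day wait for fiducials in SBRT alone. Coverage after SBRT is usually longer too, but not always. The imbalance is confined to SAEs judged unrelated, plus any bias in judging relatedness, which cannot be sized from the documents. The illustrative counts rest on an assumed rate and show only the effect of window length. The change is worth making because by-arm SAE tables are hard to interpret without it and the cost is small.

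**What to change.** In section 17.2:

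- Collect all SAEs in both arms from consent to one fixed time from randomisation that covers 30 days after the last ADT-arm treatment. Seven months is an example (7 x 365/12 = day 213, which covers days 170, 184, 198 and 205). Confirm it against the intended number of doses: seven doses at 35-day intervals would run to 6 x 35 + 30 = day 240. A late first dose would also extend it.
- Keep related-only reporting after that point.
- Tabulate SAEs by arm from randomisation within the common window, or as person-time rates, with related SAEs shown separately.
- State that SAEs within 30 days of the 24-30 month biopsy are reportable and that the biopsy does not extend the all-cause window. Change *protocol treatment* to *protocol treatment or procedure*.

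Ending the window at the 6-month post-SBRT visit would not solve the problem. On the central dates above, with no wait for fiducials, that visit falls near 25 + 183 = day 208 in SBRT alone and 109 + 183 = day 292 in the ADT arm.

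The cost is protocol wording and a few more SAE reports, mainly from SBRT alone. Some events may be learned of only at the 6-monthly visits. A window common from randomisation still leaves unequal time after SBRT (213 - 25 = 188 versus 213 - 109 = 104 days on the same dates), so tables should state the time origin. No treatment changes.
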